**VII.B.22 Who will be responsible for maintaining these use and disposition tracking records?**

N/A

**VII.B.23 Describe in detail procedures in place to limit access to authorized study personnel for the storage, control, and dispensing of the investigational devices. (For example, investigational devices are kept in a locked area away from approved devices or have a keyed interlock, and only study personnel authorized to dispense the device have the keys)**

N/A

**VII.B.24 Is the device FDA-approved for the way it will be used in this study?**

No

**VII.B.25 Is there an IDE (Investigational Device Exemption) for this device in this research project?**

No

**VII.B.29 Indicate the appropriate FDA status you and/or the sponsor are requesting for the use of this device in this study.**

Non-Significant Risk (NSR) device/software

**VII.B.31 Provide a detailed rationale for why this device meets the FDA definition of a Non-Significant Risk Device (NSR)**

Because it is not intended as an implant nor is it to be used in supporting or sustaining human life. At this time it is not of substantial importance in diagnosing, curing, mitigating or treating disease.

**VII.B.32 Provide a summary of prior investigations with this device.**

Transesophageal echocardiography is a semi-invasive, monitoring and analytic tool used to generate reproducible images of the heart and mediastinum. TEE is routinely used in cardiothoracic and interventional surgeries as well as in detecting thromboses, valvular defects and congenital heart disease. There has been expanding utilization of TEE outside of cardiac surgery as a potential haemodynamic monitor both intraoperatively and postoperatively (Pissarra 2012). While TEE is not regularly used to visualize the spinal column, it can be done with relative ease when consciously attempted (Chitilian 2006). To our knowledge, this prospective observational study will be the first attempt to deliberately image the structures within the vertebral foramen, to scan the spinal segments identified by TEE and to classify the TEE image quality by a trained sonographer. Given the nearly universal use of TEE in cardiac surgical operating rooms, in combination with the low risk of complications (Daniel 1991), potential outcomes include the use of TEE in the placement of thoracic epidural catheters, in identification of spinal cord trauma or as a monitor of intraoperative perfusion and pressure surrounding the spinal cord (Godet 1994). This could lead to improved precision, success and safety of regional anesthesia.

**VII.B.33 Have there been any prior IRB reviews (at UI or elsewhere) and/or determinations made with regard to this device?**

Yes

**VII.B.34 Provide a discussion of these reviews/determinations.**

Yes, as TEE is a standard intraoperative monitor, multiple studies have demonstrated a low rate of complications associated with TEE, deeming it safe for use in surgery (Daniel 1991).

**VII.B.35 Has the FDA made an assessment of risk with regard to this device?**

No

**VII.B.36 Has this device/software been approved by the FDA for another indication or in another form from its use in this project?**

Yes

**VII.B.37 Describe differences between approved device/software and its use in this study:**

TEE is routinely used in cardiothoracic and interventional surgeries as well as in detecting thromboses, valvular defects and congenital heart disease. In this study, TEE will not be used in a similar manner but to visualize the spinal column as can be done with relative ease when consciously attempted (Chitilian 2006). To our knowledge, this prospective observational study will be the first attempt to deliberately image the structures within the vertebral foramen, to scan the spinal segments identified by TEE and to classify the TEE image quality by a trained sonographer. Given the nearly universal use of TEE in cardiac surgical operating rooms, in combination with the low risk of complications (Daniel 1991). This could lead to improved precision, success and safety of regional anesthesia.

## VII.C. Project Description (C)

**VII.C.1 Does this project involve any research on genes or genetic testing/research?**

No

## VII.D. Project Description (D)

**VII.D.1 Check all materials/methods that will be used in recruiting subjects (you will need to attach copies of all materials at the end of the application):**

- Use of any information available to the researchers or their colleagues because this person is a patient OR use of any information considered to be Protected Health Information (PHI) OR review of patient/clinic records - Operating room schedule
- Referral from colleague - Thoracic surgery physicians and nurses may identify potential patients. Also, some patients may be identified by Pre-Anesthesia Evaluation Clinic staff.

**VII.D.2 List the individual data elements you will need to access/use from the patient or clinic records to**

**identify potential subjects for recruitment**

We will need to access patient records to check the patient's eligibility for the study by checking their surgical procedure, past medical history, counter indications for TEE use intra-operatively (esophageal trauma, lesion or disease) and age.

**VII.D.3 Describe why you could not practicably recruit subjects without access to and use of the information described above**

Many patients may be unaware that they are eligible for the study because they do not understand the routine use of TEE in the operating room. Also, patients coming to UIHC for this type of surgery come from all over Iowa and surrounding states. Recruitment of eligible patients outside of Iowa City for such a specific study population would be extremely difficult.

**VII.D.4 Describe why you could not practicably obtain authorization from potential subjects to review their patient or clinic records for recruitment purposes.**

We could not practicably obtain authorization from potential subjects to review their patient or clinic records because the population being studied is very specific. We would have to ask all patients who arrive in the thoracic surgery clinic for permission to review their charts in order to identify the possible participants needed.

**VII.D.5 Describe plans to protect the identifiers from improper use or disclosure**

The only people who will have access to the data collected for this study will be members of the research team. After data collection, the data will be immediately transferred electronically to a password protected file on a password protected computer and paper files will be kept in a locked filing cabinet in a locked office.

**VII.D.6 Describe plans to destroy identifiers at the earliest opportunity consistent with conduct of the research**

Paper identifiers will be shredded and electronic identifiers will be completely cleared from computers at the earliest opportunity consistent with the conduct of this project.

**VII.D.7 Does the research team agree that the requested information will not be reused or disclosed to any other person or entity, except as required by law, for authorized oversight of the study, or for other research for which the use or disclosure of the requested information would be permitted by the HIPAA Privacy Rule**

Yes

**VII.D.8 Will a member of the research team discuss the study with the subject in person prior to the subject agreeing to participate?**

Yes

**VII.D.9 Describe the physical location where the consent process will take place:**

In most cases the patients will be approached in the Thoracic Surgery Clinic, Pediatric Intensive Care Unit or Anesthesia Pre-Surgical Evaluation Clinic approximately 24 hours before surgery. Patients approached in the Thoracic Surgery Clinic will receive a copy of the consent form to take home with them. Those patients who are consented the day of surgery will have 1-5 hours before the surgery begins. Patients will be consented before they receive any sedation.

**VII.D.10 Will a member of the research team discuss the study with the subject by phone prior to the subject agreeing to participate?**

Yes

**VII.D.11 Describe:**

If subjects have questions for the research team they are able to contact team members by phone as provided on the consent.

**VII.D.12 Who will be involved in the [consent process](#) (including review of consent document, answering subjects' questions)?**

Name	Consent Process Involvement
[name]	Yes

**VII.D.15 Check all materials that will be used to obtain/document informed consent:**

- Consent Document

**VII.D.16 Are you requesting a [waiver of documentation](#) of consent (either no subject signature or no written document)?**

No

**VII.D.19 Before the subject gives consent to participate are there any screening questions that you need to directly ask**

**the potential subject to determine eligibility for the study?**

Yes

**VII.D.20** **List any screening questions you will directly ask the potential subject to determine eligibility.**  
We will ask if the subject has any known esophageal abnormalities, lesions, disease or other issues that would increase risks associated with transesophageal echocardiographic imaging.  
We will ask the subject if they are pregnant or incarcerated.

**VII.D.21** **Will you keep a screening log or other record that would include information on people who do not enroll in the study?**  
No

**VII.D.25** **After the subject agrees to participate (signs consent), are there any screening procedures, tests, or studies that need to be done to determine if the subject is eligible to continue participating?**  
No

**VII.D.27** **Discuss how much time a potential subject will have to agree to consider participation and whether or not they will be able to discuss the study with family/friends before deciding on participation.**  
Use of TEE is standard in cardiac surgeries. Patients who are approached in the Thoracic Surgery Clinic will have at least 24 hours to agree to consider participation in our study. These patients will receive a consent form to take home for further discussion. Patients who are approached on the day of surgery will have 1-5 hours to agree to consider participation in the study. All patients will have the opportunity to discuss with family/friends before deciding on participation.

**VII.D.28** **How long after the subject agrees to participate do study procedures begin?**  
Patients who are consented in the pre-operative clinic will have at least 24 hours between agreeing to participate and their surgery. Patients who are consented the morning of surgery will have between one and five hours from the time of consent until their surgery. Patients will be consented before they receive any sedation.

**VII.D.29** **Provide a description of the enrollment and consent process for adult subjects**

- **Describe each study population separately including control population**
- **Include when recruitment and consent materials are used**
- **Use 3rd person active voice "The Principal Investigator will identify subjects. For example, the principal investigator will identify potential subjects, the study coordinator will discuss the study with subjects over the telephone and schedule the first study visit, etc..."**
- **Describe the steps that will be taken by the research team to minimize the possibility of coercion or undue influence during the consent process**

We will identify patients who meet the inclusion criteria by reviewing the pre-operative clinic patient list and operating room schedule. All patients will be consented in the same manner.

In most cases we will approach the patients in the Thoracic Surgery Clinic, Pediatric Intensive Care Clinic or Anesthesia Pre-Surgical Evaluation Clinic at least 24 hours before surgery. We will introduce ourselves as members of the anesthesia team. We will explain the study and standard TEE procedure, including benefits and risks to the patient and provide them a copy of the consent document. The patients will have the opportunity to ask questions and discuss their participation with family or friends. Patients will also receive a copy of the consent form to take home with them. Patients who agree to participate will sign the consent document and will be provided with a copy of the consent. The consent document will contain contact information that the patient may use to contact the research team with any questions or concerns.

Those patients who are consented the day of surgery will be approached by a nurse and handed a card which states that the patient is eligible to participate in a research study. If they are interested in participating, a member of the research team will explain the study to the patient. We will explain the study, including benefits and risks, to the patient and provide them with a copy of the consent document. The patients will have the opportunity to ask questions and discuss their participation with family or friends. Patients who agree to participate will sign the consent document and will be provided with a copy of the consent. The consent document will contain contact information that the patient may use to contact the research team with any questions or concerns. Patients will have between one and five hours after consent is obtained before their surgery. No sedation will be given before the consent is obtained.

Further, in order to minimize the possibility of coercion or undue influence during the consent process, potential subjects will be reminded that participation is voluntary and choosing not to participate will not affect their surgery/care when they discuss the consent with the research team.

**VII.D.30** **Describe how you will obtain the consent of the parents or legal guardians for child/minor subjects in this study**

- **Describe each study population separately including control population**
- **Include when recruitment and consent materials are used**
- **Use FIRST person, and provide detail as to order of events**
- **Describe the steps that will be taken by the research team to minimize the possibility of coercion or undue influence during the consent process**

For children/minors who are too young to assent or consent on their own:

We will identify patients who meet the inclusion criteria by reviewing the pre-operative clinic patient list and operating room schedule. All patients or their guardians will be consented in the same manner.

In most cases we will approach the patient's guardian in the Thoracic Surgery Clinic, Pediatric Intensive Care Clinic or Anesthesia Pre-Surgical Evaluation Clinic at least 24 hours before surgery. We will introduce ourselves as members of the research study team. We will explain the study, including benefits and risks, to the the patient's guardian and provide them a copy of the consent document. Guardians will have the opportunity to ask questions and discuss the subject's participation with family or friends. Guardians will also receive a copy of the consent form to take home with them. Guardians who agree to patient participation will sign the consent document and will be provided with a copy of the consent. The consent document will contain contact information that the patient or guardian may use to contact the research team with any questions or concerns.

Those patients who are consented the day of surgery will have their guardian approached by a nurse and handed a card which states that the patients is eligible to participate in a research study. If they are interested in participating, a member of the research team will explain the study to the patient. We will explain the study, including benefits and risks, to the the patient and provide them with a copy of the consent document. The guardian will have the opportunity to ask questions and discuss their participation with family or friends. Guardians who agree to patient participation will sign the consent document and will be provided with a copy of the consent. The consent document will contain contact information that the patient may use to contact the research team with any questions or concerns. Patients will have between one and five hours after consent is obtained before their surgery. No sedation will be given before the consent is obtained.

For children/minors who will sign an assent document or are old enough to sign a consent document:

We will identify patients who meet the inclusion criteria by reviewing the pre-operative clinic patient list and operating room schedule. All patients will be consented in the same manner.

In most cases we will approach the patient and their guardian in the Thoracic Surgery Clinic, Pediatric Intensive Care Clinic or Anesthesia Pre-Surgical Evaluation Clinic at least 24 hours before surgery. We will introduce ourselves as members of the research study team. We will explain the study, including benefits and risks, to the the patient and their guardian and provide them a copy of the assent document. The patients will have the opportunity to ask questions and discuss their participation with family or friends. Patients will also receive a copy of the assent form to take home with them. Patients who agree to participate will sign the assent document and will be provided with a copy of the assent. The assent document will contain contact information that the patient may use to contact the research team with any questions or concerns.

Those patients who are assented the day of surgery will be approached by a nurse and handed a card which states that the patients is eligible to participate in a research study. If they are interested in participating, a member of the research team will explain the study to the patient. We will explain the study, including benefits and risks, to the the patient and provide them with a copy of the assent document. The patients will have the opportunity to ask questions and discuss their participation with family or friends. Patients who agree to participate will sign the assent document and will be provided with a copy of the assent form. The assent document will contain contact information that the patient may use to contact the research team with any questions or concerns. Patients will have between one and five hours after consent is obtained before their surgery. No sedation will be given before the assent is obtained.

**VII.D.31 *What are the plans for the assent process for children/minors in this study? (You may choose more than one procedure if you have different child populations in your study)***

- Children/minors will sign an assent or consent document -
- No assent procedure because some or all of the children/minors do not have the capability to assent or their capability is so limited that they cannot reasonably be consulted to provide assent-

**VII.D.36 *Provide a detailed description and rationale for each of the procedures chosen above and describe the child/minor populations to which they apply in your study.***

For those children/minors who are too young (younger than 7 years old) to assent on their own or their capability is so limited they cannot reasonably do so, their parent or guardian will consent on their behalf. All procedures and information will be explained by a member of the research team and all questions will be answered before consent is obtained.

For those children/minors that are old enough to sign an assent (7-12 years old) or consent (>12 years old) document, they will also have all procedures and information explained by a member of the research team and will be given the opportunity to ask questions before assent/consent is obtained.

**VII.D.37 *Does the study include any form of deception (e.g., providing participants with false information, misleading information, or withholding information about certain study procedures)?***

***Examples:***

- ***Procedure includes a cover story that provides a plausible but inaccurate account of the purposes of the research.***
- ***Participants will be provided with false information regarding the particular behaviors of interest in the research.***
- ***Procedures include a confederate pretending to be another participant in the study.***
- ***Participants will be told that the research includes completion of a particular task, when in fact, that task will not be administered.***
- ***Study is designed to introduce a new procedure (or task) that participants are not initially told about.***
- ***If yes, a waiver of informed consent must be requested under question IV.3.***

No

VII.E. Project Description (E)

**VII.E.1 Will subjects be randomized?**

No

**VII.E.3 Will any questionnaires, surveys, or written assessments be used to obtain data directly from subjects in this study?**

No

**VII.E.5 Does this project involve creating any audiotapes, videotapes, or photographs?**

No

**VII.E.6 Provide a detailed description in sequential order of the study procedures following the consent process - DO NOT cut and paste from the Consent Document.**

**Describe study populations separately if they will be participating in different procedures - include CONTROL population if applicable.**

**DESCRIBE:**

- **What subjects will be asked to do/what happens in the study (in sequential order)**
- **The time period over which procedures will occur**
- **The time commitment for the subject for individual visits/procedures**
- **Long-term followup and how it occurs**

The subjects of the study, scheduled to undergo cardiothoracic or interventional cardiac surgeries, will only be asked to come to their surgery. The day of surgery the patients will not be required to do anything different from standard anesthesia and surgical practice at the hospital. Subjects will come to the operating room suite and the usual monitors (electrocardiogram, non-invasive blood pressure, and oxygen saturation) will be placed. Following the routine induction of anesthesia, the Mini-Multi TEE probe (Model T6207 (21381A), Philips, Bothell, WA, USA) will be advanced to mid esophageal level in order to visualize the heart, this is standard surgical procedure in these cases. Rotation of the probe by approximately 180 degrees toward the descending aorta, with an increased gain and depth decreased to 2-3 cm, will attempt to allow for appreciation of the spinal cord and epidural space. Upon confirmation of the structures within the vertebral foramen by a trained TEE operator, an images of the spine will be captured to be later graded as high, medium or low quality by a trained sonographer. The TEE probe will then be advanced caudally and intervertebral disc spaces will be counted in order to determine the number of spinal segments that can be spanned until an image can no longer be generated. This will take approximately ten minutes, but will occur while the patient is being prepared for surgery so no additional time in the operating room will be necessary. At this point, the TEE probe will be returned to mid esophageal level to visualize the heart and the operation will proceed as usual. When looking at patient medical records, we will only collect the following data: height, weight, age, any known history of esophageal abnormalities, lesions or disease and current procedure. Ten minutes is the approximate additional time that may be required intraoperatively to observe the spinal cord on TEE but this will not extend the time in the operating room and thus no additional billing is required. No additional visits or extra time is required of the subject. There will be no necessary long-term follow up or data collection. When the patient leaves the operating room, nothing additional is required.

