**I.3** **Short Title (optional):**

**I.4** **Provide a short summary of the purpose and procedures of the study proposed in this IRB application.**

- **DO NOT include information on studies not proposed in this application.**
- **Use LAY terminology only. This must be easily understandable by IRB community members and nonscientists.**
- **DO NOT cut and paste technical abstracts from funding applications that may not be understood by a general audience.**

The aim of this prospective observational study is to assess whether transesophageal echocardiography (TEE) can be used to identify the structures within the vertebral foramen of the spinal column and to determine the range of spinal segments which can be visualized. Data will be collected from both pediatric and adult patients undergoing cardiothoracic and interventional cardiac surgeries under general anesthesia. Because use of TEE is a standard surgical procedure and because TEE will already be in place to visualize the heart, no additional processes will be required to collect data, minimizing patient risk. TEE will be monitored and controlled by a trained anesthesiologist or TEE technician and visualization of the spinal cord will be confirmed. Real-time TEE images will then be captured and later graded by a trained sonographer as high, medium or low quality. Starting at the level of the tracheal bifurcation, corresponding to thoracic vertebral level T5 (Mirajalili 2012), the TEE probe will be advanced cranially to determine the spinal levels visualized above T5 and caudally in order to determine the spinal levels below T5 that can be seen on TEE. At each level seen on TEE, pictures will be taken for confirmation.

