**I.5** **Specify your research question(s), study aims or hypotheses (do not indicate "see protocol")**

The primary outcome is to identify the spinal column and epidural space on real-time TEE image, as well as to determine the range of spinal segments that can be visually spanned by TEE.

The secondary outcomes include classification of the captured TEE image as high, medium or low quality as determined by a trained sonographer.

H0: The null hypothesis is that the spinal cord and epidural space will not be visualized on real-time TEE image.

H1: The alternative hypothesis is that the spinal cord and epidural space will be successfully confirmed by real-time TEE image in all individuals.

To test this hypothesis, both pediatric and adult patients undergoing cardiothoracic or interventional cardiac surgeries under general anesthesia will be included in the study population.

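### Sections I.4 and VII.E.6 describe two different ways of measuring the primary range of spinal segments, and the form does not say which applies

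*Combined protocol and SAP*

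**What the plan says.** I.5 makes it part of the primary outcome "to determine the range of spinal segments that can be visually spanned by TEE". It gives no rule for measuring that range.

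I.4 describes the sweep as "Starting at the level of the tracheal bifurcation, corresponding to thoracic vertebral level T5". From there "the TEE probe will be advanced cranially to determine the spinal levels visualized above T5 and caudally", the latter "in order to determine the spinal levels below T5 that can be seen on TEE". It adds: "At each level seen on TEE, pictures will be taken for confirmation".

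VII.E.6, where the form asks for the procedures in sequence, reads differently. The probe "will be advanced to mid esophageal level in order to visualize the heart" and is rotated toward the descending aorta. Once the structures are confirmed, "an images of the spine will be captured to be later graded as high, medium or low quality by a trained sonographer". Then: "The TEE probe will then be advanced caudally and intervertebral disc spaces will be counted in order to determine the number of spinal segments". The sweep ends when no further image can be obtained. The probe goes back to mid-esophageal level and the operation proceeds. The whole step is put at about ten minutes.

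VII.B.11 answers No to a separate written protocol. XI.1 plans descriptive statistics only and does not say how the range is derived.

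**The concern.** A range has an upper and a lower end. A caudal-only sweep can find the lower end but says nothing about levels visible above the start. If the start is not tied to a vertebral level, even the lower end cannot be named: the result is a number of segments below an unstated point.

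The study is purely descriptive, so this measurement is itself the result, and no between-group comparison exists in which a shared error might cancel. VII.E.6 plans no later data collection, so a level not scanned in theatre cannot be recovered. If images are kept only from the start position, no described record would allow the segment count to be checked afterwards. The number of images available for the secondary quality grading, one per patient or one per level, is also left open.

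**Working it through.** The form states no figure for the range, so there is nothing to reproduce. The check is a comparison of the two texts, followed by simple arithmetic on what each would record.

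**Side by side**

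| Element | I.4 | VII.E.6 |
|---|---|---|
| Start | Tracheal bifurcation, taken as T5 | Mid-esophageal level; no vertebral landmark named |
| Direction | Cranial and caudal | Caudal only, then the probe is returned |
| What is recorded | Levels above and below T5 | Disc spaces counted, to give a number of segments |
| Images | At each level seen | Described once, before the sweep |

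**What each procedure yields.** Assume the visible levels form one unbroken window that contains the start level. Let c be the number of levels visible cranial to the start and d the number caudal to it.

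- I.4: span = c + 1 + d, with an upper and a lower limit stated relative to T5.
- VII.E.6: d disc spaces, or d + 1 segments if the start level is counted.
- Shortfall of VII.E.6 against I.4: (c + 1 + d) − (d + 1) = c.

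The documents give no value for c. It is zero or more.

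**Dependence on the start position.** Move the start s levels caudally within the same window, so that c becomes c + s and d becomes d − s.

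- I.4 span: (c + s) + 1 + (d − s) = c + 1 + d, unchanged.
- VII.E.6 count: (d − s) + 1, lower by s.

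For a window of W levels the I.4 span is therefore W whatever the start, while the VII.E.6 count runs from W (start at the top level) down to 1 (start at the bottom level).

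**Illustration only.** Assume a visible window of T2 to T10 and a start at T5. These values are not estimates and do not come from the documents. Then c = 3 (T2 to T4) and d = 5 (T6 to T10).

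- I.4: 3 + 1 + 5 = 9 levels, T2 to T10.
- VII.E.6: 5 disc spaces, or 5 + 1 = 6 segments. Shortfall 9 − 6 = 3 = c.
- Start one level lower, at T6: c = 4 and d = 4. I.4 still gives 4 + 1 + 4 = 9; VII.E.6 gives 4 + 1 = 5.

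**Patients affected.** VI.13 plans 50 pediatric and 50 adult patients, so at most 50 + 50 = 100. A patient in whom the structures are never confirmed contributes no count under VII.E.6, so 100 is an upper bound.

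**The case against.** The best case for the plan is that only the direction of the sweep is a true contradiction.

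- **Start.** The form never says that mid-esophageal level differs from the tracheal bifurcation. I.4 could simply supply the landmark that VII.E.6 leaves out, and the caudal limit could then be named by counting down from T5.
- **Images.** I.4 describes two kinds: those to be graded, and confirmation pictures at each level. The single capture in VII.E.6 matches the first kind, and the section is silent on the second without excluding it.
- **Importance.** The hypotheses in I.5 concern whether the cord and epidural space are seen, not over what range. The analysis is exploratory, and identification of the structures does not depend on sweep direction.

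Much of this is fair. On start and images, VII.E.6 is partly silent rather than opposed, and the loss of a nameable lower limit follows only if VII.E.6 is applied without the anchor in I.4. But VII.E.6 is the sequential procedure an operator would follow, and nothing in it points back to that anchor. Nor can I.4 be set aside as a simplified lay summary, since it contains the landmark, the cranial pass and the per-level pictures that the detailed section lacks. The direction conflict stands even if the two starts coincide. A descriptive analysis does not lessen the need to define what is being described, and the range is named in the primary outcome alongside identification.

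**Conclusion.** The concern holds. The form gives two procedures for the range component of its primary outcome, they measure different quantities, and no other section chooses between them. Sweep direction is the firmest point and is sufficient by itself. The start landmark and the image rule differ as written but are partly matters of omission.

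If VII.E.6 is followed as written, the recorded count falls short of the I.4 span by c and shifts one for one with the start position. The arithmetic assumes an unbroken visible window that includes the start level. The size of c cannot be obtained from the documents and may be zero, but a caudal-only sweep could not show that it is. The ambiguity reaches every patient who contributes a range, up to 100. It should be resolved before data are collected, because levels that were not scanned cannot be recovered later.

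**What to change.** Reconcile I.4 and VII.E.6 so that every patient has the same start landmark, sweep and image-capture rule.

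- **To keep the primary outcome as stated in I.5:** carry the two-way sweep already in I.4 into VII.E.6. Record three values per patient: the start level, the number of segments seen cranial to it, and the number seen caudal to it. Report the span and the upper and lower limits relative to the landmark. State how disc spaces convert to segments, whether pictures are taken at each level, and which images are graded.
- **If only a caudal sweep is intended:** restate that part of the primary outcome as the number of segments visualized caudal to a stated start level, and remove the text in I.4 about levels above T5.

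The cost is wording in the affected sections and, under the first option, three recorded values per patient. One point needs confirmation: the ten-minute estimate in VII.E.6 accompanies a caudal-only pass, and VI.13 says the study will not prolong anesthesia or operating-room time. The investigators should confirm that the estimate still holds with a cranial pass included; the documents do not show whether it does.
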